6.1 DETERMINATION OF SAMPLE SIZE

The number of patients enrolled in the OLE study is approximately 600–700 (i.e., eligible patients from Study PRM-151-202 [Cohort A] and Study WA42293 [Cohorts B and C]). No formal sample size calculations were performed.

6.2 SUMMARIES OF CONDUCT OF STUDY

The number of patients who enroll, discontinue, or complete the study will be summarized. Reasons for premature study withdrawal will be listed and summarized. Enrollment and major protocol deviations will be listed and evaluated for their potential effects on the interpretation of study results.

6.3 SAFETY ANALYSES

The safety analyses will include all patients who receive at least one administration (full or partial dose) of PRM-151 study drug.

Safety will be assessed through descriptive summaries of exposure to PRM-151 study drug, adverse events, SAEs, AESIs, and laboratory test results. Data will be reported by cohort.

6.3.1 Adverse Events

Verbatim descriptions of TEAE will be coded using the most current version of the Medical Dictionary for Regulatory Activities (MedDRA) and adverse event severity will be graded according to NCI CTCAE v5.0 scale. A TEAE is defined as any new adverse event reported or any worsening of an existing condition on or after the first dose of study drug.

The incidence and observation time-adjusted rate will be summarized, as appropriate. In addition, separate summaries will be generated for serious adverse events, deaths, adverse events of special interest, and adverse events leading to discontinuation of PRM-151. Adverse events will be summarized by mapped term, appropriate thesaurus level, and toxicity grade.

6.3.2 Laboratory Data

Relevant laboratory data will be displayed by time, with grades identified where appropriate. Additionally, a shift table of selected laboratory tests will be used to summarize the baseline and maximum post baseline severity grade.

6.4 EFFICACY ANALYSES

Patient efficacy data will be summarized by cohort including all patients who receive at least one administration (full or partial dose) of PRM-151 study drug. Efficacy will be assessed by annual rate of change in FVC (mL), 6MWD, FVC% predicted, and DL_{CO}, time to disease progression, and survival as measured by all-cause mortality, IPF-related mortality and respiratory-related mortality. The annual rate of change in FVC

(mL), 6MWD, FVC% predicted, and DL_{CO} will be calculated using the slope from a linear mixed effect model with random intercept (subject) and random slope (time), using measurements collected at each time point in this study. Additionally, change from baseline to Weeks 52 and 104 in quantitative imaging analysis parameters of HRCT scan of the thorax will be summarized. All efficacy parameters will be summarized descriptively, and as all patients will be receiving PRM-151, there will be no hypothesis testing between treatment groups.

As is planned for the WA42293 study, in the assessment of spirometry data (FVC [mL], FVC% predicted, and DL_{CO}), all measurements that meet the minimal level of quality will be used. With respect to handling of missing data, for the purpose of determining the annual rate of change estimates, appropriate strategy will be adopted in this study for the data impacted by intercurrent events. For lung transplantation, a hypothetical strategy will be utilized where measurements collected after transplantation will not be used in the analysis, and values will be implicitly imputed from the model. For death, a composite strategy will be utilized where assessments following death will be assigned with values to designate treatment failure. Further details will be specified in the Statistical Analysis Plan. In addition, summaries using all observed data will be performed.

Kaplan-Meier estimates for the median and quartiles will be computed for time to disease progression (defined as time to first occurrence of $\geq 10\%$ absolute decline in % predicted FVC, $\geq 15\%$ relative decline in 6MWD, or death) and time to death; estimates will be presented together with their 95% confidence intervals.

6.5 EXPLORATORY EFFICACY ANALYSIS

Exploratory analyses will be performed on the following endpoints and may also be performed for additional endpoints and subgroups of interest including concurrent use of IPF treatment and geographic region:

- Change from baseline in University of California, San Diego Shortness of Breath Questionnaire (UCSD SOBQ)
- Change from baseline in St. George Respiratory Questionnaire (SGRQ) Total Score
- Time to first respiratory-related hospitalizations (defined as non-elective hospitalizations due to any respiratory cause, including acute exacerbations of IPF, or suspected acute exacerbations of IPF)
- Time to first acute exacerbation of IPF, or suspected acute exacerbation of IPF

All efficacy exploratory parameters will be summarized descriptively. For time to event endpoints, Kaplan-Meier estimates for the median and quartiles will be computed and estimates will be presented together with their 95% confidence intervals.

Further details for the exploratory analyses will be provided in the Statistical Analysis Plan.

6.6 PHARMACOKINETIC ANALYSES

The PK analysis population will consist of patients with sufficient data to determine plasma concentrations of PRM-151 at specified timepoints, unless major protocol deviations or unavailability of information (e.g., exact blood sampling time) occurred which may interfere with PK evaluation, with patients grouped according to treatment received.

Individual and mean plasma PRM-151 concentration versus time data will be tabulated and summarized descriptively. The pharmacokinetics of PRM-151 will be summarized by one or more key PK parameters (as appropriate for data collected). Estimates for these parameters will be tabulated and summarized (mean, standard deviation, coefficient of variation, median, minimum, and maximum).

Additional exploratory PK analyses will be conducted as appropriate.

6.7 IMMUNOGENICITY ANALYSES

The immunogenicity analysis population will consist of all patients with at least one ADA assessment.

The number and percentage of ADA positive patients at baseline and during the study will be tabulated by cohort. The relationship between ADA status and safety, efficacy, and PK, may be analyzed and reported via descriptive statistics.

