5.3 SAFETY ANALYSIS

The safety objective for this study is to confirm the long-term safety and tolerability of 10 mg/kg of zinpentraxin alfa administered Q4W via IV infusion plus standard of care (SOC) treatment, on the basis of the following endpoints:

- Incidence and severity of AEs, with severity determined according to the 5-point severity scale (National Cancer Institute Common Terminology Criteria for Adverse Events, Version 5.0 [NCI CTCAE, v.5.0])

- Incidence and severity of IRRs and other AEs of special interest (AESIs)
- Proportion of patients permanently discontinuing study treatment due to AEs
- Change from baseline in targeted clinical laboratory test results

Safety analyses will be based on patients from safety populations and grouped according to cohorts and the treatment groups described in Section 5.1.1.

Safety will be assessed through descriptive summary of exposure to study drug, seriousness and severity of AEs, and AESIs, changes in laboratory test results, death, discontinuation from study treatment, ECG and vital signs. These summaries will be produced for the entire study period, from the start of OLE period till the time of the snapshot or end of the study.

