5.3.7 Other Safety Endpoints

Summaries of safety data by ADA status will be provided as appropriate. See Section 5.6.5 for more details on ADA status.

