5.6.5 Immunogenicity Analyses

The following summaries will be provided for both Cohort A and Cohort B (only for patients who enrolled into the Study WA42293 prior to 1 June 2022) by the treatment group as defined in Section 5.1.1:

- Numbers and proportions of ADA-positive patients and ADA-negative patients at baseline (baseline prevalence) and after drug administration (post-baseline incidence)
- Number and percent of patients with at least one treatment-induced ADA
- Drug concentration at ADA collection timepoints

A by-patient listing of ADA status will be provided.

When determining post-baseline incidence, patients are considered to be ADA positive; if they are ADA negative or have missing data at baseline but develop an ADA response following study drug exposure (treatment-induced ADA response), or if they are ADA positive at baseline and the titer of one or more post-baseline samples is at least 0.60 titer unit greater than the titer of the baseline sample (treatment-enhanced ADA response). Patients are considered to be ADA negative if they are ADA negative or have missing data at baseline and all post-baseline samples are negative, or if they are ADA positive at baseline but do not have any post-baseline samples with a titer that is at least 0.60 titer unit greater than the titer of the baseline sample (treatment unaffected).

The relationship between ADA status and safety, efficacy, and pharmacokinetics may be analyzed and reported via descriptive statistics.

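### Safety by ADA status uses one ever-positive label per patient but counts events from OLE Day 1: biased towards ADA positives for death and discontinuation, possibly the reverse for reactions

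*Protocol*

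**What the plan says.** - **Use of ADA status.** Protocol 6.7 makes the comparison optional: "The relationship between ADA status and safety, efficacy, and PK, may be analyzed and reported via descriptive statistics". SAP 5.3.7 goes further for safety, "Summaries of safety data by ADA status will be provided as appropriate", and refers to SAP 5.6.5 for status.
- **The label.** Under SAP 5.6.5 the positive label goes to anyone meeting this condition: "if they are ADA negative or have missing data at baseline but develop an ADA response following study drug exposure (treatment-induced ADA response"). A rise of at least 0.60 unit over a positive baseline titre also qualifies. On the negative side: "Patients are considered to be ADA negative if they are ADA negative or have missing data at baseline and all post-baseline samples are negative". Also negative are patients who were positive at the start without such a rise: "if they are ADA positive at baseline but do not have any post-baseline samples with a titer that is at least 0.60 titer unit greater".
- **Population.** Protocol 6.7: "The immunogenicity analysis population will consist of all patients with at least one ADA assessment". A post-baseline sample is not required.
- **Outcome window.** SAP 5.3 runs safety summaries "from the start of OLE period till the time of the snapshot or end of the study". In SAP 5.3.2 the AE rate is events divided by total duration in the study.
- **Sampling.** Protocol Appendices 3 and 4 schedule ADA at Day 1 and Weeks 4, 12 and 24, plus an unscheduled sample before a reload within the first 24 weeks. Appendix 1 lists no routine ADA sample at the treatment discontinuation visit.
- **Triggered sampling.** Protocol 5.1.4 (with Table 2) and Appendix 1 also call for ADA samples at Grade 2 or higher IRRs and at suspected anaphylaxis or hypersensitivity, with no Week 24 limit.

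Neither document gives a landmark, a time-varying status or a split of patient-time at seroconversion.

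**The concern.** The label depends on samples taken after follow-up has begun, yet it is applied to all follow-up from Day 1. A patient found positive at Week 24 must have survived on treatment for 24 weeks. That event-free time is credited to the positives. A patient who dies or stops after a negative Week 4 sample goes to the negatives. For terminal outcomes this is immortal-time bias.

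For non-terminal events two effects work the other way. A reaction at a Day 1, 3 or 5 infusion counts as an ADA-positive event if the patient converts at Week 24. In addition, a reaction prompts an ADA test that a patient without a reaction would not have had.

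Protocol 1.3.1 names ADAs as a possible threat to efficacy, with possible cross-reaction against endogenous pentraxin-2. A distorted table could hide a harm in deaths and discontinuations, or suggest one in reactions.

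**Working it through.** The plan has no figure of its own to reproduce: no tests and no ADA effect are stated. The size therefore rests on assumed inputs.

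**Inputs**
- Sampling times v = 4/52, 12/52 and 24/52 years (Appendices 3 and 4).
- Proportion converting, p: 7.8%, from 6 ADA-positive patients in the Phase II PRM-151 group (Protocol 1.3.1). The group size of 77 is implied by 2 patients being 2.6%, and 6/77 = 7.8%. An upper assumption of 20% is also used. Conversion is spread evenly over the three visits.
- Rate of death or permanent discontinuation, λ: not in the documents; assumed 10 to 25 per 100 patient-years, constant. Follow-up ends at the event.
- True effect of ADA: none.

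**Formulas**, per patient, follow-up T years
- Events in positives: E₊ = (p/3) Σ [exp(−λv) − exp(−λT)]
- Time in positives: Y₊ = (p/3) Σ {v·exp(−λv) + [exp(−λv) − exp(−λT)]/λ}
- Totals: E = 1 − exp(−λT) and Y = E/λ. Negatives are the remainder.

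**Worked case**: 1,000 patients, λ = 0.10, p = 7.8%, T = 1, so 1,000p/3 = 26.
- exp(−λv) = 0.99234, 0.97719, 0.95490; exp(−λT) = 0.90484.
- E₊ = 26 × (0.08750 + 0.07235 + 0.05006) = 5.46
- Y₊ = 26 × (0.9513 + 0.9490 + 0.9413) = 73.88 patient-years; rate 7.39 per 100
- Negatives: (95.16 − 5.46)/(951.63 − 73.88) = 89.70/877.74; rate 10.22 per 100
- Ratio: 7.39/10.22 = **0.72**, where the truth is 1.0.

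Losses before Week 4 have no post-baseline sample. Leaving them unclassified removes 7.66 events and 0.29 patient-years from the negatives: 82.04/877.45 = 9.35 per 100, ratio **0.79**.

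Splitting time at the first positive sample gives positives 5.46/54.58 = 10.0 per 100 and negatives 89.70/897.05 = 10.0 per 100, ratio **1.00**.

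**Range** (first figure: early losses counted negative; second: left unclassified)

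| p | λ | 52 weeks | 104 weeks | 5 years |
|---|---|---|---|---|
| 7.8% | 0.10 | 0.72 / 0.79 | 0.85 / 0.89 | 0.93 / 0.95 |
| 7.8% | 0.25 | 0.72 / 0.79 | 0.84 / 0.88 | 0.91 / 0.94 |
| 20% | 0.10 | 0.69 / 0.77 | 0.83 / 0.88 | 0.92 / 0.95 |
| 20% | 0.25 | 0.69 / 0.76 | 0.82 / 0.87 | 0.90 / 0.93 |

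**Sensitivity to timing.** With early losses counted negative, the 52-week ratio is 0.77 to 0.80 if 60% of conversions appear at Week 4 and 20% at each other visit. It is 0.60 to 0.64 if 60% appear at Week 24. A simulation of deaths alone, using the 2 to 5 year median survival in Protocol 3.3.3 and a constant conversion rate, gave 0.64 at 1 year, 0.78 to 0.80 at 2 years and 0.85 to 0.89 at 5 years.

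**If ADA were harmful.** Replace λ by 1.5λ after the positive sample. E₊ becomes (p/3) Σ exp(−λv)·{1 − exp[−1.5λ(T − v)]}, and the bracket in Y₊ is divided by 1.5λ. With early losses counted negative, the true ratio of 1.5 then appears as 1.02 to 1.08 at 52 weeks and 1.21 to 1.27 at 104 weeks. Splitting time returns 1.5.

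**Reactions.** Simulation over 2 years with no true effect, 7.8% converting by Week 28 at a rate that then continues, 0.06 reactions and 0.15 treatment stops per patient-year (both rates assumed). With scheduled samples only, the risk ratio is 1.10 and the rate ratio 0.99. With reaction-triggered samples added, they are 2.15 and 1.90. Splitting time does not cure this if triggered samples still set status: the ratio is 1.05 to 1.07 if conversion stops at Week 24, but 2.6 to 2.7 if it continues.

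**The case against.** The strongest reply is that this is optional, descriptive output. Protocol 6.7 says may, SAP 5.3.7 says as appropriate, no tests are planned, and SAP 5.6.5 introduces its rule for post-baseline incidence. The AE listing also carries onset day, so the time order could be recovered. This lowers the weight but does not remove the point: SAP 5.3.7 sends the reader to 5.6.5 for status, no other definition is given, and SAP 5.3.2 does not divide patient-time.

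The bias also fades. It arises only up to Week 24, and the final analysis follows the last patient's last visit, expected by the end of 2028. That stands. SAP 5.1 sets no 24-week analysis, so the ratios of about 0.4 at that point are not relied on. It does name the parent-study unblinding and, if needed, Week 52 of Cohort B.

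Four stronger readings are tempting, and the documents do not support them:
- **The plan makes antibodies look harmless throughout.** Triggered samples and pre-conversion events push reaction comparisons the other way.
- **Everyone who stops or dies early is filed as negative.** The negative rule refers to post-baseline samples; a patient with none is undefined.
- **Status builds up over the whole extension.** Scheduled sampling ends at Week 24. Sampling throughout would have given a larger bias, 0.39 to 0.44 in the simulation of deaths.
- **FVC and 6MWD slopes by ADA status are biased.** Nothing here shows it.

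**Conclusion.** The point holds for death and permanent discontinuation by ADA status. Followed as written, SAP 5.3, 5.3.2, 5.3.7 and 5.6.5 together favour ADA positives, with a rate ratio of about 0.7 to 0.8 at 52 weeks and 0.8 to 0.9 at 104 weeks when the truth is 1.0, and about 0.9 or higher at 5 years. For IRRs and hypersensitivity the distortion can run in the opposite direction and roughly double the ratio.

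These sizes rest on assumed event, conversion and reaction rates and on constant hazards. They also treat everyone as a new converter, although Cohort A and the former active arm enter already exposed. They show direction and order of size and are not forecasts. With 7.8% converting there would be few positives, so any observed ratio would also be imprecise. The change should be made before the tables are programmed, but no main conclusion of the study depends on it.

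**What to change.** Amend SAP 5.6.5 and 5.3.7 as follows.

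1. For AE, discontinuation and death rates by ADA status, count events and patient-time as ADA positive only from the first positive or treatment-enhanced scheduled sample, and as negative before it.
2. Do not let reaction-triggered samples set status in the main comparison; list them separately. State how the unscheduled pre-reload samples are handled.
3. Show patients with no post-baseline sample as unclassified, and patients already positive at OLE baseline as their own group. At present the latter are classed negative unless their titre rises by 0.60 unit.
4. Keep the per-patient label for the incidence table.
5. If survival or progression is shown by ADA status, use time-varying status, or a Week 24 landmark as a supportive analysis.
6. State as a limitation that seroconversion after Week 24 is largely unobserved.

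The cost is SAP wording and a little more programming, with no new samples. A landmark table omits the first 24 weeks; the time-split tables still cover them.

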6.8 BIOMARKER ANALYSES

Biomarkers will be assessed at baseline and subsequent timepoints following administration of PRM-151. Biomarkers will be presented as absolute value over time and/or percent change relative to baseline over time. Biomarker levels at baseline or over time may be compared with efficacy or safety measurements to assess prognostic or predictive properties.

Descriptive or summary statistics will be used to describe biomarker assessments.

6.9 HEALTH STATUS UTILITY ANALYSES

Annual rate of change in EQ-5D-5L health utility index-based and VAS scores will be summarized descriptively.

7. DATA COLLECTION AND MANAGEMENT

7.1 DATA QUALITY ASSURANCE

The Sponsor will be responsible for data management of this study, including quality checking of the data. Data entered manually will be collected via EDC through use of eCRFs. Sites will be responsible for data entry into the EDC system. In the event of discrepant data, the Sponsor will request data clarification from the sites, which the sites will resolve electronically in the EDC system.

The Sponsor will produce an EDC Study Specification document that describes the quality checking to be performed on the data. Central laboratory data, spirometry, HRCT, DL_{CO} and other non-eCRF data will be sent directly to the Sponsor, using the Sponsor's standard procedures to handle and process the electronic transfer of these data.

eCRFs and correction documentation will be maintained in the EDC system's audit trail. System backups for data stored by the Sponsor and records retention for the study data will be consistent with the Sponsor's standard procedures.

PRO data will be collected through the use of an electronic device provided by a vendor (see Section 7.3 for details).

7.2 ELECTRONIC CASE REPORT FORMS

eCRFs are to be completed through use of a Sponsor-designated EDC system. Sites will receive training and have access to a manual for appropriate eCRF completion. eCRFs will be submitted electronically to the Sponsor and should be handled in accordance with instructions from the Sponsor.

All eCRFs should be completed by designated, trained site staff. eCRFs should be reviewed and electronically signed and dated by the investigator or a designee.

At the end of the study, the investigator will receive patient data for his or her site in a readable format that must be kept with the study records. Acknowledgement of receipt of the data is required.

7.3 ELECTRONIC PATIENT REPORTED OUTCOME DATA

An electronic device will be used to capture PRO data. The device is designed for entry of data in a way that is attributable, secure, and accurate, in compliance with FDA regulations for electronic records (21 CFR Part 11). The data will be transmitted to a centralized database maintained by the electronic device vendor.

The electronic data will be available for view access only, via a secure web server. Only identified and trained users may view the data, and their actions will become part of the audit trail. The Sponsor will have view access only. System backups for data stored by the Sponsor and records retention for the study data will be consistent with the Sponsor's standard procedures.

Once the study is complete, the data, audit trail, and trial and system documentation will be archived. The investigator will receive patient data for the site in both human and machine-readable formats that must be kept with the study records as source data. Acknowledgement of receipt of the data is required. In addition, the Sponsor will receive all data in a machine-readable format.

7.4 SOURCE DATA DOCUMENTATION

Study monitors will perform ongoing source data verification and review to confirm that critical protocol data (i.e., source data) entered into the eCRFs by authorized site personnel are accurate, complete, and verifiable from source documents.

Source documents (paper or electronic) are those in which patient data are recorded and documented for the first time. They include, but are not limited to, hospital records, clinical and office charts, laboratory notes, memoranda, patient-reported outcomes, evaluation checklists, pharmacy dispensing records, recorded data from automated instruments, copies of transcriptions that are certified after verification as being accurate and complete, microfiche, photographic negatives, microfilm or magnetic media, X-rays, patient files, and records kept at pharmacies, laboratories, and medico-technical departments involved in a clinical trial.

Before study initiation, the types of source documents that are to be generated will be clearly defined in the Trial Monitoring Plan. This includes any protocol data to be entered directly into the eCRFs (i.e., no prior written or electronic record of the data) and considered source data.

Source documents that are required to verify the validity and completeness of data entered into the eCRFs must not be obliterated or destroyed and must be retained per the policy for retention of records described in Section 7.6.

To facilitate source data verification and review, the investigators and institutions must provide the Sponsor/ or delegate CRO direct access to applicable source documents and reports for trial-related monitoring, Sponsor audits, and IRB/EC review. The study site must also allow inspection by applicable health authorities.

